10.1.4 Nodal Partial Response with Lymphocytosis

In this study, patients who achieve PR criteria for lymphadenopathy and/or splenomegaly, but have a lymphocyte count which is elevated and/or does not meet PR criteria (and may be significantly above baseline), will be considered to have nodal PR with lymphocytosis.

10.1.5 Stable disease

Patients who have not achieved CR, PR, or nodal PR with lymphocytosis, and who have not exhibited progressive disease, will be considered to have stable disease (which is equivalent to a nonresponse).

10.1.6 Treatment failure

Responses that should be considered clinically beneficial include CR, PR and nodal PR with lymphocytosis; all others (eg, stable disease, nonresponse, progressive disease, or death from any cause) should be rated as a treatment failure.

10.1.7 Time to progression, progression-free survival, and overall survival

Time to progression (TTP) is defined as the time from study entry until objective disease progression (see above). Progression-free survival (PFS) is defined as the time from study entry until objective disease progression or death. Overall survival is defined as the time from study entry until death from any cause, and is measured in the intent-to-treat population.

10.1.8 Relapse

Relapse is defined as a patient who has previously achieved the above criteria of a CR or PR or nodal response with lymphocytosis, but after a period of 6 or more months, demonstrates evidence of disease progression as described above.

10.1.9 Refractory disease

CONFIDENTIAL

This document is confidential. Do not disclose or use except as authorized.

Refractory disease is defined as treatment failure or disease progression within 6 months to the last antileukemic therapy.

10.1.10 Minimal residual disease

The complete eradication of the leukemia is an obvious desired endpoint. New detection technologies, such as multicolor flow cytometry and real-time quantitative PCR, have determined that many patients who achieved a CR by the 1996 NCI-WG guidelines have detectable MRD. Either 4-color flow cytometry (MRD flow) or allele-specific oligonucleotide PCR is reliably sensitive down to a level of approximately one CLL cell in 10,000 leukocytes. As such, patients will be defined as having a clinical remission in the absence of MRD when they have blood or marrow with less than one CLL cell per 10,000 leukocytes.

Those patients undergoing bone marrow biopsy for evaluation of CR should have a sample sent for 4 color MRD flow.

10.2 Duration of Response

Duration of overall response: The duration of overall response is measured from the time measurement criteria are met for CR or PR (whichever is first recorded) until the first date that recurrence or PD is objectively documented, taking as reference for PD the smallest measurements recorded since the treatment started.

Duration of clinical benefit: The duration of clinical benefit is measured from the time measurement criteria are first met for CR, PR or nodal PR with lymphocytosis, until the first date that recurrent disease is objectively documented.

Duration of overall complete response: The duration of overall CR is measured from the time measurement criteria are first met for CR until the first date that recurrent disease is objectively documented.

Duration of stable disease: Stable disease is measured from the start of the treatment until the criteria for progression are met, taking as reference the smallest measurements recorded since the treatment started

10.3 Response Review

10.3.1 Central review of the CT scans is required for all scans (screening, cycle 2 day 22, cycle 4 day 22, cycle 10 day 1 (final restaging), and at disease progression). These scans should be burned onto CD and sent via FedEx to the Project Manager at DFCI, ATTN: (Project Manager), [name], Boston, MA 02215. The scan will then be reviewed at the Tumor Imaging Metrics Core at DFCI.

CONFIDENTIAL

This document is confidential. Do not disclose or use except as authorized.

11. ADVERSE EVENT REPORTING REQUIREMENTS

11.1 Definitions

11.1.1 Adverse Event (AE)

An adverse event (AE) is any undesirable sign, symptom or medical condition or experience that develops or worsens in severity after starting the first dose of study treatment or any procedure specified in the protocol, even if the event is not considered to be related to the study.

Abnormal laboratory values or diagnostic test results constitute adverse events only if they induce clinical signs or symptoms or require treatment or further diagnostic tests.

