6. EXPECTED TOXICITIES AND DOSING DELAYS/DOSE MODIFICATIONS

Dose delays and modifications will be made using the following recommendations. Toxicity assessments for non-hematologic toxicity will be done using the CTEP Version 4.0 of the NCI Common Terminology Criteria for Adverse Events (CTCAE) which is identified and located on the CTEP website at:

http://ctep.cancer.gov/protocolDevelopment/electronic_applications/ctc.htm. Hematologic toxicity will be evaluated according to the IWCLL 2008 guidelines as outlined below and in Appendix C.

If possible, symptoms should be managed symptomatically. In the case of toxicity, appropriate medical treatment should be used (including anti-emetics, anti-diarrheals, etc.).

CONFIDENTIAL

This document is confidential. Do not disclose or use except as authorized.

All adverse events experienced by participants will be collected from the time of the first dose of study treatment, through the study and until the final study visit. Participants continuing to experience toxicity at the off study visit may be contacted for additional assessments until the toxicity has resolved or is deemed irreversible.

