11.1.2 Serious adverse event (SAE)

A serious adverse event (SAE) is any adverse event, occurring at any dose and regardless of causality that:

- Results in death
- Is life-threatening. Life-threatening means that the person was at immediate risk of death from the reaction as it occurred, i.e., it does not include a reaction which hypothetically might have caused death had it occurred in a more severe form.
- Requires or prolongs inpatient hospitalization (i.e., the event required at least a 24-hour hospitalization or prolonged a hospitalization beyond the expected length of stay). Hospitalization admissions and/or surgical operations scheduled to occur during the study period, but planned prior to study entry are not considered SAEs if the illness or disease existed before the person was enrolled in the trial, provided that it did not deteriorate in an unexpected manner during the trial (e.g., surgery performed earlier than planned).
- Results in persistent or significant disability/incapacity. Disability is defined as a substantial disruption of a person's ability to conduct normal life functions.
- Is a congenital anomaly or birth defect; or
- Is an important medical event when, based upon appropriate medical judgment, it may jeopardize the participant and require medical or surgical intervention to prevent one of the outcomes listed above. Examples of such medical events include allergic bronchospasm requiring intensive treatment in an emergency room or at home; blood dyscrasias or convulsions that do not result in inpatient hospitalization, or the development of drug dependency or drug abuse.

Laboratory and Other Safety Assessment Abnormalities Reported as AEs and SAEs

- Any abnormal laboratory test results (hematology, clinical chemistry, or urinalysis) or other safety assessments (e.g., ECGs, radiological scans, vital signs measurements), including those that worsen from baseline, and felt to be clinically significant in the medical and scientific judgment of the investigator **are** to be recorded as AEs or SAEs.

CONFIDENTIAL

This document is confidential. Do not disclose or use except as authorized.

- Grade 4 uncomplicated hematologic toxicities that are common in this patient population do NOT need to be reported as SAEs or reported to the DFCI IRB, unless resulting in hospital admission or if the treating investigator deems it appropriate to report.

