- All events requiring patients to come off study due to liver toxicity must be recorded as an SAE.
- However, any clinically significant safety assessments that are associated with the underlying disease, unless judged by the investigator to be more severe than expected for the subject's condition, are **not** to be reported as AEs or SAEs.
- B cell depletion, lymphopenia, IgG below LLN, low CD19+ count, and hypogammaglobulinemia due to treatment with ofatumumab are **not** to be reported as AEs or SAEs.
- Infusion related AEs may lead to a prolonged infusion time. Overnight stay at the hospital due to slow infusion rate is **not** to be reported as a SAE.
- Pregnancy complications and elective terminations for medical reasons must be reported as an AE or SAE. Spontaneous abortions must be reported as a SAE. Any SAE occurring in association with a pregnancy, brought to the investigator's attention after the subject has completed the study and considered by the investigator as possibly related to the investigational product, must be promptly reported to Novartis

Not included as SAEs:

- routine treatment or monitoring of the studied indication, not associated with any deterioration in condition, or for elective procedures
- elective or pre-planned treatment for a pre-existing condition that did not worsen
- emergency outpatient treatment for an event not fulfilling the serious criteria outlined above and not resulting in inpatient admission
- respite care

Disease-Related Events and/or Disease-Related Outcomes Not Qualifying as SAEs

An event which is part of the natural course of the disease under study (i.e., disease progression) does not need to be reported as a SAE. However, if the progression of the underlying disease is greater than that which would normally be expected for the subject, ends in death, or if the investigator considers that there was a causal relationship between treatment with investigational product or protocol design/procedures and the disease progression, then this must be reported as an SAE.

Pregnancy

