14.2 Analysis of Secondary Endpoints

Other Secondary Objectives:

- To determine the CR rate and PFS of ofatumumab and idelalisib.
- To determine the ORR, CR and rate of nodal PR with lymphocytosis for idelalisib given alone for 2 months.
- To assess the safety of ofatumumab and idelalisib in combination.
- To determine whether clinical response correlates with known CLL molecular prognostic factors.
- To determine whether the use of CT scans in response assessment improves the predictive power of ORR for progression-free or overall survival.
- To determine whether serum ofatumumab levels in vivo predict response.
- To assess whether idelalisib alters the flow cytometric phenotype of circulating CLL cells.
- To assess whether in vivo treatment with idelalisib alters CLL cell sensitivity to therapy with antibodies or other kinase inhibitors
- To assess pharmacodynamic markers of PI3 kinase inhibition including AKT phosphorylation, production of T cell chemokines and response to CXCR 4/5
- To determine whether response or resistance correlates with genetic alterations in PIK3CA or PIK3CD or other genes
 - To assess the clonal dynamics of CLL in peripheral blood vs bone marrow, and during therapy with idelalisib.

Secondary Analysis:

The CR rate of combination therapy, ORR rate, and rate of nodal PR with lymphocytosis for idelalisib given alone for 2 months will be summarized as numbers and percentages. The Kaplan Meier method will be used to estimate the median progression free survival. The number and percent of patients who experience toxicities on combination therapy after at least one dose of treatment will also be summarized. Associations of clinical response rate and known prognostic factors will be assessed using Fisher's exact test.

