3.10 Safety Assessments and Toxicity Monitoring

The study teams at all participating institutions are responsible for protecting the safety, rights and well-being of study participants. Recording and reporting of adverse events that occur during the course of a study help ensure the continuing safety of study participants.

All participants receiving investigational agents and/or other protocol mandated treatment will be evaluated for safety. The safety parameters include all laboratory tests and hematological abnormalities, physical examination findings, and spontaneous reports of adverse events reported by participants. All toxicities encountered during the study will be evaluated according to the NCI criteria specified in the protocol. Life-threatening toxicities must be reported immediately to the DF/HCC Sponsor via the Coordinating Center.

Additional safety assessments and toxicity monitoring will be outlined in the protocol.

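### Conflicting rules for when a laboratory abnormality is an adverse event leave capture of untreated, asymptomatic grade 3 or higher cytopenias to site practice, and Section 14.2 does not name the source of its toxicity rates

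*Combined protocol and SAP*

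**What the plan says.** Several statements bear on the same laboratory data.

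- **Section 11.1.1** (adverse event definition): abnormal results "constitute adverse events only if they induce clinical signs or symptoms or require treatment or further diagnostic tests". Grade plays no part.
- **Section 11.1.2** (laboratory abnormalities): abnormal hematology, chemistry and other results "felt to be clinically significant in the medical and scientific judgment of the investigator" are to be recorded as adverse events or serious adverse events. Symptoms, treatment or further tests are not required.
- **Section 11.1.2** also has two carve-outs. "Grade 4 uncomplicated hematologic toxicities that are common in this patient population do NOT need to be reported as SAEs", with hospital admission or the investigator's own decision as exceptions. Separately, "any clinically significant safety assessments that are associated with the underlying disease" are not reported unless they are more severe than expected.
- **Section 6**: "Hematologic toxicity will be evaluated according to the IWCLL 2008 guidelines". Section 11.2 likewise grades hematologic toxicity on the CLL-specific scale. That scale is based on counts and has no symptom or treatment condition.
- **Appendix D Section 3.10**: "The safety parameters include all laboratory tests and hematological abnormalities".
- **Section 14.2**: "The number and percent of patients who experience toxicities on combination therapy after at least one dose of treatment will also be summarized". It names no data source, grade threshold or scale.

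**The concern.** Sections 11.1.1 and 11.1.2 set different tests for the same decision, and nothing says which governs. The wording of 11.1.1 is exclusive, so 11.1.2 cannot simply be read as an addition to it. An investigator who follows 11.1.1 literally leaves out an asymptomatic, untreated grade 3 cytopenia. One who follows 11.1.2 may include it.

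Safety is a secondary objective of a small single-arm study, so its hematologic toxicity rates will be read against outside experience. If the rates depend on each site's G-CSF habits or on individual judgment, they are not reproducible. Compared with a tabulation of the counts themselves, a filter of this kind can only lower them.

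**Working it through.** The plan states no figure that this point would change. The check is a comparison of the rules, followed by an illustration of size.

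**Step 1. One case under each rule.** Take a grade 3 neutropenia found on a routine blood count in a patient with no symptoms, no G-CSF and no extra test.

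| Rule | Counted? |
|---|---|
| 11.1.1 | No |
| 11.1.2, investigator judgment | Yes if judged clinically significant, otherwise no |
| 11.1.2, disease-related exclusion | No if attributed to CLL and not worse than expected |
| Sections 6 and 11.2, count-based grading | Graded 3 by the count alone |
| Appendix D 3.10 | Within the stated safety scope |
| 14.2 | Not stated |

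**Step 2. Can the case occur?** Yes. Table 6 maintains the idelalisib dose at grade 3 and leaves G-CSF to the investigator. Section 6.2 says ofatumumab is generally not held for myelosuppression. Table 10 already schedules hematology weekly through cycle 4 day 22, so a low count need not lead to an additional test. At grade 4 the room is narrower: Table 6 asks that G-CSF be considered, and Section 6.2 provides growth factor and transfusion support as needed. Neither makes treatment automatic.

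Liver tests differ. Under Section 6.2, a grade 3 or higher transaminase rise leads to holding idelalisib and repeat testing, so it meets even the 11.1.1 definition.

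**Step 3. Does the recording rule reach the analysis?** Probably. Section 11.4.4 puts non-serious adverse events on the toxicity case report forms, and Appendix D Section 3.11 says adverse events are noted on the toxicity forms. The submission schedule in Section 12.1.2 lists an adverse event form but no laboratory form. Section 14.2 does not settle the matter.

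**Step 4. Size.** Inputs:

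- n = 27, the number at which enrollment stopped (Section 14.1).
- p = 8% for neutropenia and 4% for thrombocytopenia, the grade 3 or higher rates in CLL patients on idelalisib (Section 6.1.1).
- s = the share of such events that goes unrecorded. The documents do not give it, so it is an assumption, run from 0 to 1.

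Formulas: expected events = n × p; expected loss = n × p × s; fall in the rate = p × s; chance that none is recorded = (1 − p(1 − s))^n.

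Expected events are 27 × 0.08 = 2.16 and 27 × 0.04 = 1.08.

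| | s = 0 | s = 0.5 | s = 1 |
|---|---|---|---|
| Neutropenia: patients lost | 0 | 1.08 | 2.16 |
| Neutropenia: fall in rate (points) | 0 | 4 | 8 |
| Neutropenia: chance none recorded | 10.5% | 33.2% | 100% |
| Thrombocytopenia: patients lost | 0 | 0.54 | 1.08 |
| Thrombocytopenia: fall in rate (points) | 0 | 2 | 4 |
| Thrombocytopenia: chance none recorded | 33.2% | 58.0% | 100% |

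One patient is 1/27 = 3.7 points. The s = 1 column is the extreme in which every event is asymptomatic, untreated and not further tested, and 11.1.1 alone decides recording. Where investigators apply 11.1.2, the loss lies between zero and that extreme.

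**The case against.** The strongest reply is that 11.1.2, under its own laboratory heading, already requires clinically significant hematology results to be recorded, and that many investigators would judge a grade 3 or 4 cytopenia significant. The waiver of serious adverse event reporting for uncomplicated grade 4 hematologic toxicity points the same way, since it would hardly be needed if such counts were not adverse events. Section 14.2 also speaks of toxicities rather than adverse events, and Section 6 grades those by count. Appendix D Section 3.10 is a general monitoring statement, not a recording or tabulation rule.

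Much of this stands, and it rules out three stronger readings.

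- A reader might infer that untreated, asymptomatic cytopenias necessarily drop out of the toxicity rates. They do not, because 11.1.2 can still capture them.
- A reader might infer that another section promises toxicity rates covering every laboratory result. None does. Appendix D Section 3.10 describes scope, and Section 14.2 leaves the source open.
- A reader might add the two losses, about 3 patients of 27 or 11 points. These are separate rates, and the sum also assumes that different patients are affected. Neither expected rate can fall by more than its own 8 or 4 points.

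The reply does not remove the conflict. It shows that a sensible investigator could apply 11.1.2, not that the plan makes every investigator do so.

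**Conclusion.** The point holds as a reporting weakness of minor severity. Two rules conflict on when a laboratory abnormality is an adverse event, the safety scope in Appendix D is wider than both, and the analysis section does not name its source. Capture of asymptomatic, untreated grade 3 or higher cytopenias may therefore vary by site and investigator, most plausibly at grade 3, and the reported rates may be too low.

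The illustrated size rests on four assumptions:

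- background rates from idelalisib experience outside this study apply to these previously untreated patients;
- all 27 enrolled patients form the denominator, although Section 14.2 refers to toxicity on combination therapy, which fewer may have reached;
- the toxicity table is built from the adverse event forms;
- the unrecorded share is unknown and could be anything from 0 to 1.

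The primary response analysis is unaffected.

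**What to change.** 1. Reconcile Section 11.1.1 with 11.1.2 so that one rule governs when a laboratory abnormality is recorded as an adverse event, and make clear how Appendix D Section 3.10 relates to it.

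2. In Section 14.2, tabulate hematologic toxicity as the worst grade per patient from the protocol-scheduled counts on the IWCLL scale, beside the rates from the adverse event forms. Apply the baseline evaluability footnotes of the appendix table. Flag cytopenias attributed to the disease, so that the exclusion in 11.1.2 remains visible.

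3. Before doing so, settle which table is meant. Sections 6 and 11.2 and Appendix D Section 3.11 refer to Appendix C for hematologic grading, but Appendix C is the PML questionnaire and the grading table is in Appendix B. The grade 4 platelet cut-off also differs (25K in Table 6, 20,000/mm³ in Appendix B), and the two must be reconciled.

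The cost is modest but goes beyond programming. Because Section 12.1.2 lists no laboratory form, the counts may have to be retrieved from source, for at most 27 patients. Reported hematologic toxicity may come out somewhat higher. The tabulation in item 2 changes reporting only, and hepatic rates need no similar step for grade 3 or higher events.

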11.1.2 Serious adverse event (SAE)

A serious adverse event (SAE) is any adverse event, occurring at any dose and regardless of causality that:

- Results in death
- Is life-threatening. Life-threatening means that the person was at immediate risk of death from the reaction as it occurred, i.e., it does not include a reaction which hypothetically might have caused death had it occurred in a more severe form.
- Requires or prolongs inpatient hospitalization (i.e., the event required at least a 24-hour hospitalization or prolonged a hospitalization beyond the expected length of stay). Hospitalization admissions and/or surgical operations scheduled to occur during the study period, but planned prior to study entry are not considered SAEs if the illness or disease existed before the person was enrolled in the trial, provided that it did not deteriorate in an unexpected manner during the trial (e.g., surgery performed earlier than planned).
- Results in persistent or significant disability/incapacity. Disability is defined as a substantial disruption of a person's ability to conduct normal life functions.
- Is a congenital anomaly or birth defect; or
- Is an important medical event when, based upon appropriate medical judgment, it may jeopardize the participant and require medical or surgical intervention to prevent one of the outcomes listed above. Examples of such medical events include allergic bronchospasm requiring intensive treatment in an emergency room or at home; blood dyscrasias or convulsions that do not result in inpatient hospitalization, or the development of drug dependency or drug abuse.

Laboratory and Other Safety Assessment Abnormalities Reported as AEs and SAEs

- Any abnormal laboratory test results (hematology, clinical chemistry, or urinalysis) or other safety assessments (e.g., ECGs, radiological scans, vital signs measurements), including those that worsen from baseline, and felt to be clinically significant in the medical and scientific judgment of the investigator **are** to be recorded as AEs or SAEs.

CONFIDENTIAL

This document is confidential. Do not disclose or use except as authorized.

- Grade 4 uncomplicated hematologic toxicities that are common in this patient population do NOT need to be reported as SAEs or reported to the DFCI IRB, unless resulting in hospital admission or if the treating investigator deems it appropriate to report.
- All events requiring patients to come off study due to liver toxicity must be recorded as an SAE.
- However, any clinically significant safety assessments that are associated with the underlying disease, unless judged by the investigator to be more severe than expected for the subject's condition, are **not** to be reported as AEs or SAEs.
- B cell depletion, lymphopenia, IgG below LLN, low CD19+ count, and hypogammaglobulinemia due to treatment with ofatumumab are **not** to be reported as AEs or SAEs.
- Infusion related AEs may lead to a prolonged infusion time. Overnight stay at the hospital due to slow infusion rate is **not** to be reported as a SAE.
- Pregnancy complications and elective terminations for medical reasons must be reported as an AE or SAE. Spontaneous abortions must be reported as a SAE. Any SAE occurring in association with a pregnancy, brought to the investigator's attention after the subject has completed the study and considered by the investigator as possibly related to the investigational product, must be promptly reported to Novartis

Not included as SAEs:

- routine treatment or monitoring of the studied indication, not associated with any deterioration in condition, or for elective procedures
- elective or pre-planned treatment for a pre-existing condition that did not worsen
- emergency outpatient treatment for an event not fulfilling the serious criteria outlined above and not resulting in inpatient admission
- respite care

Disease-Related Events and/or Disease-Related Outcomes Not Qualifying as SAEs

An event which is part of the natural course of the disease under study (i.e., disease progression) does not need to be reported as a SAE. However, if the progression of the underlying disease is greater than that which would normally be expected for the subject, ends in death, or if the investigator considers that there was a causal relationship between treatment with investigational product or protocol design/procedures and the disease progression, then this must be reported as an SAE.

Pregnancy

Any pregnancy that occurs during study participation must be reported to the overall Principal Investigator and to Novartis. To ensure subject safety, each pregnancy must be reported to Novartis within 2 weeks of learning of its occurrence. The pregnancy must be followed up to determine outcome (including premature termination) and status of mother and child. Pregnancy complications and elective terminations for medical reasons must be reported as an AE or SAE. Spontaneous abortions must be reported as an SAE.

CONFIDENTIAL

This document is confidential. Do not disclose or use except as authorized.

Any SAE occurring in association with a pregnancy, brought to the investigator's attention after the subject has completed the study and considered by the investigator as possibly related to the investigational product, must be promptly reported to Novartis.

In addition, the investigator must attempt to collect pregnancy information on any female partners of male study subjects who become pregnant while the subject is enrolled in the study. Pregnancy information must be reported to Novartis as described above.

